4.3. EXCLUSION CRITERIA	9
4.4. WITHDRAWAL CRITERIA	9
5. ADVERSE EVENTS	9
5.1. DEFINITIONS	9
5.2. REPORTING PROCEDURES	10
6. ASSESSMENT AND FOLLOW-UP	10
7. STATISTICS AND DATA ANALYSIS	11
8. REGULATORY ISSUES	12
8.1. ETHICS APPROVAL	12
8.2. CONSENT	12
8.3. CONFIDENTIALITY	12
8.4. INDEMNITY	13
8.5. SPONSOR	13
8.6. FUNDING	13
8.7. AUDITS	13
9. STUDY MANAGEMENT	13
10. PUBLICATION POLICY	13
11. REFERENCES	13

GLOSSARY OF ABBREVIATIONS

BCT	Behavioural Change Technique
ICL	Imperial College London
NHS	National Health Service
NHSBSP	NHS Breast Screening Programme

NHSE	NHS England
RCT	Randomised Controlled Trial
SMS	Short Message Service

KEYWORDS

Breast cancer screening, uptake, behavioural science, SMS messaging

STUDY SUMMARY

TITLE Investigating the use of behavioural science informed messages to facilitate attendance at Breast Cancer Screening

DESIGN Randomised Controlled Trial

AIMS To determine the impact of SMS messages, and a video developed using behavioural science upon the uptake

[figure not shown]
OUTCOME MEASURES Primary: percentage uptake of the invitation to screen. Secondary: percentage uptake of the invitation to screen amongst population subgroups (e.g. by demographic factors, and by invitation type).

POPULATION All women aged between 50 and 70, invited to screen in the London breast cancer screening region.

ELIGIBILITY Eligible to attend the NHSBSP in London during the study period.

DURATION 6 months

REFERENCE DIAGRAM

1. INTRODUCTION

1.1. BACKGROUND

Breast cancer is the most common cancer in the UK, with 1 in 8 women affected during their lifetime(1). Whilst survival rates are high, the 5-year survival rate is 72% higher with the earliest stage breast cancer, compared to the latest disease stage(2). The NHS Breast Cancer Screening Programme (NHSBSP) invites women aged 50 to 70 years old every three years to a mammogram. By enabling earlier detection, it is estimated that the NHSBSP saves 1300 lives per year(3).

Despite the potential benefits of breast cancer screening, attendance is falling. Coverage rates have fallen nationally by 1.3% between 2016 and 2020. London has shown particularly poor rates (67.3%), with coverage in 2020 below the acceptable target of 70%(4). The COVID-19 pandemic has exacerbated these trends with an estimated 1 million mammograms missed, due to the cessation of screening to minimise transmission risk (5)(6). Counteracting these trends is a significant public health priority.

Furthermore, there is increasing concern regarding the socio-demographic inequalities in breast screening uptake. For example, the odds of attendance amongst those from the most

deprived areas is 5% lower than those from less deprived areas (7)(8). In addition, in one study in London, the adjusted odds of attendance were almost three times higher amongst White British, compared to Asian women, and six times higher than Black women(9). The barriers faced by these groups need to be appreciated, and any intervention to increase attendance ensure that inequalities are not widened(10).

Behavioural Science is a field of study concerning understanding the processes underpinning human action(11). Behavioural theories, such as the Capability Opportunity Motivation-Behaviour (COM-B) model (12, 13), have been used to understand the determinants of several health behaviours including handwashing and smoking (14, 15). Recent studies have shown the application of behavioural science to screening may also facilitate uptake of invitations (16). In one study by Kerrison et al. the use of a reminder prompt SMS increased uptake by 5% (17). However, the use of plain text messages limits which behavioural determinants can be feasibly addressed, and what techniques can be used. Video messages can allow for more complex and a broader range of behavioural change techniques (BCTs) to be incorporated, and therefore have greater impact upon attendance.

1.2. RATIONALE FOR CURRENT STUDY

Whilst behavioural science-informed messages have previously been trialled by groups to facilitate breast screening attendance, their effectiveness has been variable (18). One of the reasons for this, is that SMS messages are of limited length and formatting capability, thus restricting the number of BCTs that can be included. Moreover, some behavioural techniques are more complex than others, and plain text can limit the extent to which these can be feasibly incorporated. Video messaging provides a delivery mechanism that may enable more complex, and different combinations to be trialled. There is however, a paucity of data regarding the impact of sending a video-based behavioural science message upon attendance rates at breast cancer screening programmes. This study looks to investigate the impact of a video-message, compared to behavioural science-based SMS messages and standard reminder SMS.

2. STUDY OBJECTIVES

The primary object is to determine the impact of behavioural science informed (1) video and (2) SMS messages compared to usual care, upon uptake of breast cancer screening. Secondary objectives involve how this impact on attendance differs between population subgroups including people from differing demographic groups and people invited to open, as opposed timed appointments (see Study Design).

3. STUDY DESIGN

This study will be conducted as a randomised control trial (RCT) in the London screening region of the NHSBSP. The study will last over 6 months. The administrative hub for the NHSBSP in London is based at the Royal Free Hospital, who will oversee invitation scheduling, message delivery and outcome data collation through their existing delivery systems.

Participants will be randomised using simple randomisation method in a 1:1:1 fashion to either intervention arm or usual care. Randomisation will utilise a computerised system in which each participant who is due for screening in the study period is randomly allocated a

number corresponding to the message they will receive. This will be undertaken by the screening hub, and will be passed on to the message delivery service who will ensure the correct template is sent.

Written invitations are sent, as standard practice, by the NHSBSP to invite women to either (1) an appointment at a set time, date and location (so-called timed invitations) or (2) to call and book an appointment (or open invitation). Following this, as part of usual care, those selected for open invitations will receive a first SMS 7 days post written invitation. They will then receive two SMS reminders, 7 days and 2 days prior to the appointment, once it has been booked. Those who receive timed invitations will just receive the two reminder messages, 7 and 2 days prior to the appointment. The decision to offer an individual a timed or open invitation is made by the screening service based on their covid-19 recovery process, and will not be altered by this project.

This RCT will involve randomising participants to receive the usual care messages (according to the timings outlined above), a plain text SMS incorporating BCTs or the BCT SMS with a new link to a video incorporating more BCTs (see **figure 1 for message content in each of the three trial arms**).

The content of the intervention messages, and the video have been developed through extensive Patient and Public Involvement and Engagement work including 10 interviews, 2 focus groups and 2 co-design workshops. Members of the public have been consulted throughout the process, especially regarding the representations of individuals in the video, and the message content. The feedback received has been used to alter the materials, and further feedback received. Through this iterative approach we have ensured content is appropriate. We have also sought feedback from members of the Oremi centre (a mental health day service specifically for African Caribbean and Arabic Speaking adults) and Gendered Intelligence (a trans-led organisation to improve the quality of life of trans people) to ensure individuals from these groups are happy with representations. Screening commissioners, led by [name] (NHS England Breast Screening Lead, London), have also approved this content. The NHS Identity team have provided approvals for the use of NHS logos/branding, and the team at London Northwest Healthcare NHS Trust approved the use of their name.

The video will be hosted on a private page on the Imperial College London website, which will be available only to those who have been sent the link. The video will be translated into several languages, with voice overs also available in different languages, to ensure people from a diverse background are able to understand the content.

After 3 months from the initial written invitations, data will be collated from the breast screening hub regarding whether an individual attended an appointment and whether the messages were successfully sent. This will be repeated at 6 months corresponding to the key performance indicator of the service.

Figure 1. Message content for timed and open invitations for the trial arms (a) control, (b) plain text SMS with BCTs and (c) BCT SMS with new link to BCT video.

Reminders at 7 and 2 days prior to appointment		
a) Control	b) Behavioural SMS	c) Behavioural SMS + Video


Don't forget your breast screening appointment is at 10:36 am on 26/10/2021 at Edgware Community Hospital. To re-arrange or cancel your appointment call [name] or visit www.london-breastscreening.org.uk For further info please click here: https://youtu.be/7CAJqKnxKa4
	
Following the breast cancer screening letter you received, don't forget your appointment is at 10:36am on 26/10/2021 at Edgware Community Hospital. Detecting breast cancer early gives you the best chance to fully recover. To find out why we're inviting you and what to expect watch this video: https://youtu.be/7CAJqKnxKa4 To re-arrange or cancel your appointment call [name]
	
Following the breast cancer screening letter you received, don't forget your appointment is at 10:36am on 26/10/2021 at Edgware Community Hospital. Detecting breast cancer early gives you the best chance to fully recover. To find out why we're inviting you and what to expect watch this video: https://imperial.ac.uk/ABBS To re-arrange or cancel your appointment call [name]

---	--	--

Message sent 7 days after the open invitation to book an appointment		
a) Control	b) Behavioural SMS	c) Behavioural SMS + Video

Breast Screening appointments have changed. You will have received a letter on how to book an appointment. Please call the London Breast Screening Hub on [name] or visit www.london-breastscreening.org.uk to arrange an appointment at your nearest location. For further info please click here: https://youtu.be/7CAJqKnxKa4"
	
Breast Screening appointments have changed. You will have received a letter on how to book an appointment. Please call the London Breast Screening Hub on [name] or visit www.london-breastscreening.org.uk to arrange an appointment locally.
 
Detecting breast cancer early gives you the best chance to fully recover. To find out why we're inviting you and what to expect watch this video: https://youtu.be/7CAJqKnxKa4
	
Breast Screening appointments have changed. You will have received a letter on how to book an appointment. Please call the London Breast Screening Hub on [name] or visit www.london-breastscreening.org.uk to arrange an appointment locally.
 
Detecting breast cancer early gives you the best chance to fully recover. To find out why we're inviting you and what to expect watch this video: https://imperial.ac.uk/ABBS

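### Every arm carries a video link, so arm b is not a plain-text arm, and the only video question the trial can answer is new versus existing video

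*Combined protocol and SAP*

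**What the plan says.** Section 1.2 argues that an SMS has little room for behavioural change techniques (BCTs) and that video lifts this limit. It then sets out the comparison: "This study looks to investigate the impact of a video-message, compared to behavioural science-based SMS messages and standard reminder SMS".

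Section 2 gives the primary objective as the effect of "behavioural science informed (1) video and (2) SMS messages compared to usual care, upon uptake of breast cancer screening". Both comparisons named there are against usual care.

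Section 3 describes the two intervention arms as "a plain text SMS incorporating BCTs or the BCT SMS with a new link to a video incorporating more BCTs", and the Figure 1 caption lists the arms as "a) control, (b) plain text SMS with BCTs and (c) BCT SMS with new link to BCT video". In the column headings of Figure 1, only arm c has the word video.

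The message templates in Figure 1 read as follows, for both the appointment reminders and the message that follows an open invitation:

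- Arm a: "For further info please click here: https://youtu.be/7CAJqKnxKa4"
- Arm b: "To find out why we're inviting you and what to expect watch this video: https://youtu.be/7CAJqKnxKa4"
- Arm c: "To find out why we're inviting you and what to expect watch this video: https://imperial.ac.uk/ABBS"

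**The concern.** A reader of sections 1.2 and 3 would take arm b to be text without video, and would take c versus b to show what video adds to a behavioural text. The templates do not deliver that contrast, because women in arm b are also told to watch a video.

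What is at stake is the interpretation. If c and b turn out alike, the labels invite the conclusion that video adds nothing to a behavioural SMS. If b does better than a, they invite crediting the wording alone, although some of the gain may come from more women opening the existing video. Either conclusion could mislead a screening service that is choosing between rewriting its texts and commissioning a video.

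**Working it through.** No arithmetic applies, and the sample size in section 7 plays no part in the point. The check is to set the six templates side by side and list what changes in each contrast.

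**Step 1: is there an arm without a video?** Arm a does not call its link a video, but the address is the one that arm b introduces with "watch this video: https://youtu.be/7CAJqKnxKa4". So arms a and b point to the same existing video. Arm c points to a different address on the college site. Three arms by two message types gives six templates, and all six contain a link. No arm is free of video.

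**Step 2: what differs in each pairwise contrast?**

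- *b versus a.* The wording changes, including an added sentence on the benefit of early detection. The existing video moves from an optional source of information to something the woman is told to watch. In the reminders, the booking website given in arm a is dropped; the open-invitation message keeps it. The video itself does not change.
- *c versus b.* The message text is identical in both message types and only the address differs. The page behind it differs too. Section 3 places the new video on a private college page, with translations and voice-overs in several languages, and section 6 adds an optional feedback questionnaire there. The contrast is therefore the new video with its page against the existing YouTube video.
- *c versus a.* All of the above change together.

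None of the three contrasts has video on one side and no video on the other.

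**Step 3: can the analysis separate the parts?** The variables listed for extraction in section 7 include no link clicks and no viewing. The per-protocol analysis in section 3.1 depends on whether the SMS was received, not on whether the video was watched. The questionnaire in section 6 is optional and anonymous, and sits on the page used only by arm c. Because arms a and b share one address, even a total view count for the existing video would not tell those two arms apart.

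**Step 4: which stated aims are affected?**

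- *Section 2 (each package against usual care).* Usual care already includes the existing link, so b versus a and c versus a are sound randomised comparisons of what the service would send with what it sends now.
- *Section 1.2 (video message against behavioural SMS).* This is the aim that the arms do not match.
- *The plain-text label for arm b.* It appears in the Section 3 description and the Figure 1 caption. Section 2 does not use it, and section 1.2 uses the term only for a general limit of text messages.

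**The case against.** The strongest reply is that this is a pragmatic trial in a service that already sends a video link, and that its primary objective is each package against usual care. On that reading nothing is broken. This part stands. A reader might infer from the templates that the whole trial can only compare one video with another; section 2 does not support that, because b versus a and c versus a answer its question.

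A second reply is that the interest lies in a video built on BCTs, not in video as a medium, and that c versus b isolates such a video under identical wording. That is a fair account of what c versus b does, and a useful contrast for this service. It is also a reason to describe it in those terms, which section 1.2 does not do.

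A third reply is that the plan discloses the position: section 3 speaks of a new link, section 8.2 of a different video, and the templates are printed in full. These do hint that a video is already in use. They do not say that arm b carries and promotes it, and the plain-text label says the opposite. If that label refers only to the format of the SMS, arm c is plain text as well, and the label distinguishes nothing.

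Finally, the misreadings described above are risks, not stated plans. Section 7 names a chi-squared test but does not say which arms are compared or how a result will be read. The documents therefore do not show that a null c-versus-b result would be reported as video having no effect; they only leave nothing in place to prevent it.

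**Conclusion.** The point holds for the video question and for the labels. The plain-text description of arm b is wrong against the trial's own templates. The comparison in section 1.2 is in fact the new BCT video and its page against the existing video, and b versus a mixes behavioural wording with a stronger prompt to watch the existing video. The primary-objective comparisons with usual care stay valid, and the sample size is untouched.

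The mismatch runs through all six templates, so it reaches everyone to whom a trial message is sent; by the estimate in section 3.1 the service holds mobile numbers for 80% of invitees. No bias in uptake can be put in figures, because the documents give no viewing rate and no effect for either video. Equal uptake in b and c would be compatible with both videos working equally well or with neither working, and the planned data could not tell these apart.

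This rests on two assumptions: that the printed templates are what will be sent, and that the shared address leads to a video in arm a as arm b says it does.

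**What to change.** 1. In the Section 3 description of the arms and in the Figure 1 caption and column labels, rename arm b *behavioural SMS promoting the existing screening video* and arm c *behavioural SMS promoting the new BCT video*. Drop the plain-text label.
2. In section 1.2, replace the comparison of a video message with behavioural SMS by a comparison of the new with the existing video.
3. Add a short statement of what each contrast may conclude:
   - b versus a: behavioural wording, including the stronger prompt to watch the existing video and, in the reminders, removal of the website address;
   - c versus a: the whole package;
   - c versus b: the new video and its page (host, translations) against the existing video, under identical wording.

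Do not move arm b's video to the college host to tidy up c versus b. Control would stay on YouTube, so the move would put a host difference into b versus a, which is a primary-objective comparison.

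The cost is a few lines of protocol text: no extra women, no new data and no change to randomisation. The downside is a narrower claim about video. Relabelling does not make the video-versus-text question answerable; that would need a comparator whose messages carry no video link, which is a different design.

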3.1. STUDY OUTCOME MEASURES

The primary outcome of this study is the percentage uptake of breast cancer screening, three months after the initial invitation letter. This will be reported as both intention-to-treat and per protocol, according to whether the SMS messages were received. Currently it is estimated that the screening service has access to 80% of mobile numbers of invitees.

Secondary outcomes will involve how the uptake differs according to:

- demographics (e.g. ethnicity, deprivation)
- invitation type (open and timed invitation)
- attendance history (previous non-attendee, recurrent attendee, first-time invitee)

We will also repeat the primary analysis to determine the uptake at 6 months. These timepoints were chosen firstly from the literature which suggests the impact of behavioural interventions occurs in the acute decision phase, but also following discussion with the screening service where 6 monthly reporting coincides with a key performance indicator.

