4.4. WITHDRAWAL CRITERIA

As messages will be sent through the NHSBSP and undertaken as part of the usual care process the withdrawal criteria will match those of the screening service. Individuals can opt-out of both messaging or screening at any time throughout the process and will be excluded. No data for those who highlight opt-outs will be held or analysed by researchers. The opt-out decision will be retained by screening services, and they will not be contacted with the messages. This process involves either indicating opt-out through the national data opt-out (should they wish not for their data to be used) or by contacting the London breast cancer screening service using the details provided on their invitation letter. Those who have opted out will not have data passed to researchers for analysis. However, following pseudo-anonymisation it will not be possible for researchers to identify individuals who wish to have their data withdrawn.

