7. STATISTICS AND DATA ANALYSIS

There will be three trial arms in this RCT. Based upon previous studies, and what would constitute a clinically meaningful effect size a power calculation has been conducted (18). Assuming 5% type 1 error probability, 80% power, and an effect size of 3%, results in a minimum sample size of 2797 people per study arm (8391 in total). Chi-squared non-parametric statistic will be used to determine whether effects are significant. Secondary outcomes will examine the impact upon attendance amongst subgroups including those with different invitation type and from different demographic groups. A regression model will be developed to test these secondary hypotheses.

Data flow for this project is demonstrated in **figure 2**.

Figure 2 Demonstrating data flow of project.

Variables that will be extracted for analysis will include:

1. Demographics
 - Age at invitation
 - Index of Multiple Deprivation (derived from postcode)
 - Ethnicity
 - Previous attendee/non-attendee/first-time invitee
2. Invitation
 - Invitation type (open or timed)
 - Screening service location
3. Outcome
 - Attendance at booked appointment

Data and all appropriate documentation will be stored for a minimum of 10 years after the completion of the study, including the follow-up period.

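### Does leaving the received messages undefined spoil the per-protocol comparison of uptake?

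*Combined protocol and SAP*

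**What the plan says.** Section 3.1 makes uptake three months after the invitation letter the primary outcome and adds: "This will be reported as both intention-to-treat and per protocol, according to whether the SMS messages were received". The next sentence reads: "Currently it is estimated that the screening service has access to 80% of mobile numbers of invitees". Neither sentence says how many messages must arrive, and neither analysis is named as leading.

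Section 3 sets the message schedule. Under usual care, "those selected for open invitations will receive a first SMS 7 days post written invitation". Then: "They will then receive two SMS reminders, 7 days and 2 days prior to the appointment, once it has been booked". Timed invitees get only the two reminders. In Figure 1, the panel titled "Message sent 7 days after the open invitation to book an appointment" shows different text in each arm, so allocation can influence booking.

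For data, section 3 says the hub will supply "whether an individual attended an appointment and whether the messages were successfully sent". The variable list in section 7 has attendance but no message-status field. Section 7 adds nothing about the per-protocol set. Its sample-size paragraph assumes "80% power, and an effect size of 3" per cent.

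**The concern.** Booking happens after randomisation and, for open invitees, after an SMS that differs by arm. If a woman had to receive all three messages to enter the per-protocol set, every open invitee who never booked would drop out. The set would then be selected on a step between intervention and outcome, and the arms would no longer be comparable by randomisation.

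The error could go either way. A message that persuades hesitant women to book would add bookers less likely to attend, lowering attendance among those retained. A message that works only through the reminders would look stronger than it is, because non-bookers leave the denominator. Section 3.1 places both analyses under the primary outcome, so two disagreeing results could appear with no written rule on which one stands.

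**Working it through.** The plan has no figure of its own for the per-protocol set, so there is none to reproduce. The check asks how far each reading moves the estimate.

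**Inputs.** The message schedule and the 80% mobile coverage come from sections 3 and 3.1. The 3% effect comes from section 7. It is read here as 3.0 percentage points and applied to women reached by SMS. All other inputs are assumed, because the document does not give them: 60% of open invitees book (b), 85% of bookers attend (a), extra bookers attend at 60% (q), and timed uptake is 70%. The share of open invitations (s) is also not given and is varied.

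**All three messages required, open invitations only.** Control uptake is 0.60 × 0.85 = 51.0%. With the effect it is 54.0%. The per-protocol rate is attendees divided by bookers.

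- Control: 0.51 / 0.60 = 85.0%.
- Effect through booking only (5 points of extra bookers, 0.05 × 0.60 = 0.03): 0.54 / 0.65 = 83.1%, a difference of **-1.9**.
- Effect through reminders only: 0.54 / 0.60 = 90.0%, a difference of **+5.0**.
- Booking only, with extra bookers attending like the others (q = 85%): **0.0**.

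**All three required of open invitees, both invitation types pooled, timed women also +3.0.**

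- Control = (0.51s + 0.70(1 - s)) / (0.60s + 1 - s).
- Intervention = (0.54s + 0.73(1 - s)) / (Bs + 1 - s), with B = 0.65 for booking only and B = 0.60 for reminders only.

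| Open share | Control | Booking only | Reminders only |
|---|---|---|---|
| 25% | 72.5% | 74.8% (+2.3) | 75.8% (+3.3) |
| 50% | 75.6% | 77.0% (+1.3) | 79.4% (+3.75) |
| 75% | 79.6% | 79.7% (0.0) | 83.9% (+4.3) |
| 80% | 80.6% | 80.3% (-0.3) | not needed |

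With an equal timed effect, the sign changes only just above 75% open. With no effect in timed women, booking only gives 0.660 / 0.9125 = 72.3% at 25% open (-0.2, true +0.75) and 0.620 / 0.825 = 75.2% at 50% open (-0.5, true +1.5).

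**Every message due must arrive, open invitations only, 5% independent failure per message.** Bookers are kept with probability 0.95³ = 0.857 and non-bookers with 0.95.

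- Control: 0.51 × 0.857 / (0.60 × 0.857 + 0.40 × 0.95) = 48.9%.
- Booking only: 0.54 × 0.857 / (0.65 × 0.857 + 0.35 × 0.95) = 52.0%, a difference of **+3.1**.
- Reminders only: 0.54 × 0.857 / (0.60 × 0.857 + 0.40 × 0.95) = 51.8%, a difference of **+2.9**.

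**Mobile number held, or first message delivered.** Membership does not depend on booking, so the open-invitation contrast stays at 51.0% against 54.0%, or **+3.0**.

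**Ordinary dilution.** With 80% coverage and no effect in unreached women, +3.0 among women reached is 0.80 × 3.0 = +2.4 in all randomised women. The two analyses would therefore differ somewhat even with a perfectly defined set.

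**Which reading fits the text.** Timed invitees are never sent the day-7 message, so a flat three-message rule would exclude all of them. The messages that count must be judged by what each woman was due, and section 3 makes reminders due to open invitees only after booking. A three-message rule would also remove women who booked less than seven days ahead and attended. The delivery data described in section 3 record whether messages went out successfully, which again points to delivery of what was due.

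**The case for a change.** The strongest opposing case is that some readings are harmless and one is badly biased, so the choice should be fixed before the data are seen. The sentence on mobile numbers estimates coverage and is not a membership rule. Section 3.1 speaks of messages received, section 3 of messages successfully sent, and the section 7 variable list includes neither. With no stated precedence, an analyst could choose both the reading and the lead result afterwards.

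The wording gap is real, and so is the mismatch between these sections. The arithmetic under the three-message reading is also correct, and if timed women gain nothing, a small sign change can occur at modest open shares. What does not stand is the step from a missing definition to a likely bias, because the harmful reading runs against the message schedule.

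Precedence is also less open than it looks. Section 3.1 lists intention-to-treat first, and section 8.2 justifies the trial as a test of overall effect across the population. The intention-to-treat set is incomplete only for opt-outs: "Those who have opted out will not have data passed to researchers for analysis". Finally, a bookers-only set would be conspicuous. On the assumed rates, control uptake among open invitees would read 85.0% per protocol against 51.0% by intention-to-treat, with 60% and 65% of women retained in the two arms under booking only.

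**Conclusion.** No change to the plan is needed. The per-protocol set lacks a written definition, but the sensible ways to fill it keep non-bookers in and leave the estimate at or within about 0.2 points of the true +3.0 (at 5% delivery failure per message). Only a rule requiring all three messages does real damage: -1.9 to +5.0 with open invitations alone, or +1.3 to +3.75 at 25% to 50% open with an equal timed effect. Nothing in the document specifically supports that rule. The sizes rest on assumed booking, attendance and timed-uptake rates and an unknown open share, so they illustrate direction and cannot carry severity. The conclusion depends on analysts judging receipt against the messages each woman was due, or against having a mobile number. The intention-to-treat comparison, which answers the population-level question, is unaffected by any reading.

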4.3. EXCLUSION CRITERIA

The exclusion criteria will match those used by the NHSBSP, as all invitations will come directly from the programme, as per usual care. These include:

- Previous attendance at breast screening in the current (3-year cycle)
- Opted out of receiving SMS messages
- Opted out of screening
- Previous bilateral mastectomy

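### The 2,797 per arm makes no allowance for the roughly 20% of invitees who cannot be texted; if the 3 points is the effect in women messaged, intention-to-treat power at that minimum is about 61–63%, not 80%

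*Combined protocol and SAP*

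**What the plan says.** Section 3 (Study design) allocates every woman due for screening in the study period: "Participants will be randomised using simple randomisation method in a 1:1:1 fashion to either intervention arm or usual care". Its Figure 1 shows that the arms differ only in the wording of the texts and the video link they carry.

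Section 4.2 lists age, residence and registered sex, and does not ask for a mobile number. The only exclusion in section 4.3 that concerns messaging is "Opted out of receiving SMS messages".

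Section 3.1 plans both an intention-to-treat and a per-protocol report of uptake at three months, the second according to whether the messages were received. It then adds: "Currently it is estimated that the screening service has access to 80% of mobile numbers of invitees".

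Section 7 has one power statement, a 5% type 1 error with "80% power, and an effect size of 3%, results in a minimum sample size of 2797 people per study arm". It gives no control uptake, no sidedness and no allowance for women who cannot be messaged. The variables listed there for extraction do not include whether a number was held.

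**The concern.** A woman with no number on file has the same experience in all three arms, so she adds nothing to the difference between arms but is counted in both the numerator and the denominator of uptake. An effect confined to women who are messaged therefore shrinks in proportion to coverage when everyone randomised is analysed. A sample size that uses the unshrunken effect is too small for that analysis, and a useful message could be reported as ineffective.

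The per-protocol report does not repair this. Receipt is determined after randomisation. Under section 3, women with open invitations get the 7-day and 2-day reminders only once they have booked, so receipt of those reminders depends on a step towards the outcome itself. A comparison restricted on that basis loses the protection of randomisation.

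**Working it through.** **Inputs.** Section 7: type 1 error 5%, power 80%, effect 3% (read as percentage points), 2,797 per arm. Section 3.1: numbers held for 80%. Not stated, so inferred: control uptake and sidedness. Assumed: no effect in women without a number, and the same control uptake with or without one.

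**1. Reproduce 2,797.** Unpooled normal approximation, n = (z_α + z_β)² × [p₁(1−p₁) + p₂(1−p₂)] / d².

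- One-sided, 70% v 73%: (1.6449 + 0.8416)² = 6.1826; 0.2100 + 0.1971 = 0.4071; n = 6.1826 × 0.4071 / 0.0009 = 2,796.6, so 2,797 exactly. The 70% appears in section 1.1 as the acceptable coverage target, not as an input to the calculation.
- Two-sided, 78.5% v 81.5%: (1.9600 + 0.8416)² = 7.8489; 0.1688 + 0.1508 = 0.3196; n ≈ 2,787, close to 2,797. The documents nowhere give 78.5%.
- Two-sided at 70% needs about 3,550. At the 67.3% London coverage in section 1.1, n is about 2,946 one-sided or 3,740 two-sided. None of these matches.

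The exact match leaves no room for inflation for non-receipt.

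**2. Dilute the effect.** If 3 points applies only to women messaged: 0.8 × 3 + 0.2 × 0 = 2.4 points. If 3 points is the all-invitee difference, the effect in women reached must be 3 / 0.8 = 3.75 points.

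**3. Power at 2,797 per arm for 2.4 points.** Power = Φ(d/SE − z_α), SE = √{[p₁(1−p₁) + p₂(1−p₂)] / n}.

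- One-sided, 70% v 72.4%: SE = √(0.4098 / 2,797) = 0.01210; 0.024 / 0.01210 = 1.983; Φ(1.983 − 1.645) = 0.63.
- Two-sided, 78.5% v 80.9%: SE = √(0.3233 / 2,797) = 0.01075; 0.024 / 0.01075 = 2.232; Φ(2.232 − 1.960) = 0.61.

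**4. Numbers needed for 80% power at 2.4 points.**

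- One-sided, 70%: 6.1826 × 0.4098 / 0.000576 ≈ 4,399 per arm.
- Two-sided, 78.5%: 7.8489 × 0.3233 / 0.000576 ≈ 4,405 per arm.

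Either is about 1.57–1.58 times the undiluted number.

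**5. Count the minimum on women with a number.** 2,797 / 0.8 = 3,496.25, so about 3,497 randomised per arm. In the one-sided 70% case the comparison of women with a number then has 80% power for 3 points. The all-invitee comparison has SE = √(0.4098 / 3,497) = 0.01083, and Φ(0.024 / 0.01083 − 1.645) = 0.72.

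**The case against.** The strongest reply is that 3 points may already be the difference across all invitees. Section 7 ties it to earlier studies and to clinical meaning, the outcome is uptake of the invitation, and section 8.2 defends testing the messages at population level. On that reading no power is lost. This stands: the documents do not settle the matter. What remains is an unstated requirement of 3.75 points in women reached, in a trial where every arm already receives reminders and only wording and a link change.

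Second, 2,797 is called a minimum. The population is all eligible women invited in London over six months, and no planned total or cap is given. Actual power could be higher, and about 4,400 per arm would restore 80% under either reproducing set of assumptions. This also stands. The minimum is nonetheless the figure offered as delivering 80%.

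Third, a reader might put power at about 51%, the two-sided figure at 70% control uptake and 2.4 points, and blame missing numbers for all of it. That mixes two issues. A two-sided test at 70% has only about 70% power with 2,797 per arm before any dilution. Dilution alone accounts for 80% to 63% in the one-sided case.

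Fourth, the plan discloses the 80% and already collects whether messages were sent. That shows awareness, but sending status is known only after randomisation and does not correct the sample size. The 80% is itself an estimate of number availability, not of delivery.

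**Conclusion.** Established from the documents: women without a number are randomised and counted under intention-to-treat, and the sample size has no allowance for them. The loss of power is conditional. It is 80% to about 63% (one-sided, 70% v 73%) or about 61% (two-sided, 78.5% control uptake) if three things hold: the 3 points refers to women messaged, the effect is nil in the other 20%, and recruitment stops at 2,797 per arm. If the 3 points refers to all invitees, there is no loss.

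A reader might infer that the trial is underpowered as it will be run. The documents do not support that, because they give neither the population for the 3 points nor the planned total. Nor do they require the primary analysis to be confined to women with a number: that would change the estimand, and section 8.2 gives reasons for the population-level one. This is an unstated assumption that should be resolved, not an error in the arithmetic of 2,797.

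**What to change.** 1. Add to the section 7 extraction list a flag for a mobile number on record at randomisation.
2. In section 3.1, replace the receipt-based per-protocol analysis with an analysis by allocated arm in all randomised women with that flag, reported beside the all-invitee intention-to-treat result. The flag is fixed before allocation, so the comparison remains randomised. The sponsor may choose which is primary, but should say so in advance.
3. In section 7, state the population, control uptake and sidedness that the 3 points assumes. If it refers to women messaged, count the 2,797 minimum on women with a number (about 3,497 randomised per arm at 80% coverage) and restate the all-invitee power at 2.4 points. If it refers to all invitees, state the 3.75 points this implies in women reached.

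Cost: one extra field from the screening hub and new wording in two sections. The flagged analysis applies only to the roughly 80% who can be messaged, and the stated power for all invitees may look less favourable.
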